#### **9.4. Planned Interim Analysis**

An interim analysis in support of a CE Mark submission will be conducted to analyze initial subjects randomized to the treatment arm only with respect to efficacy and safety. This interim analysis is not intended to support a decision to continue or to discontinue the trial, or to implement any modifications to trial procedures.

To alleviate potential statistical and operational bias that may be introduced, the execution of the interim analysis shall be a completely confidential process to the study team. All sponsor staff, staff contracted by the sponsor, and investigator staff directly involved in the conduct of the ongoing IDE trial will remain blind to the process and results of the analyses, with the exception of contracted resources involved in the execution of the interim analysis and submission of the results on behalf of the sponsor.

Endpoints to be evaluated using descriptive statistics are as follows:

- Primary efficacy: Time to Ambulation
- Secondary efficacy: Total Post Procedure Time, Time to Hemostasis, Time to Discharge Eligibility, Time to Discharge
- Primary safety: rate of major complications related to the access site
- Secondary safety: rate of minor complications related to the access site

In addition, device success and procedure success will be evaluated, as well as patient experience survey data.

Randomization: This is a single-arm analysis, therefore subjects randomized to control arm will be excluded.

Sample Size: 30-40 sequential subjects randomized to treatment arm from up to 7 centers.

A final clinical report will be prepared at the conclusion of the interim analysis by an agent of the sponsor who is independent from the conduct of the study. The report will be unblinded following the collection of the last patient's procedure data.

### **10. Data Management – Data Collection and Processing**

Standardized eCRFs will be utilized by all participating sites, refer to the Manual of Operations for specifications and instructions. Investigators are responsible for the accurate completion and timely submission of the data collected during the trial. All data from the trial will be entered into eCRFs via a secure, web-based system with password protection. Incoming data will be automatically

reviewed to identify inconsistent or missing data and any adverse events. Any data issues are to be promptly addressed with the Investigator by the CRO. Quality assurance procedures will be established to ensure that complete, accurate and timely data are submitted, that protocol requirements are followed and that complications, adverse events and adverse device effects are correctly reported and investigated, as appropriate. Investigators are to maintain all source documents as required by the protocol, including laboratory results, supporting medical records, and signed Informed Consent forms. The source documents will be used during the regular monitoring visits to verify information from the database against data contained on the completed eCRFs.

The Principal Investigator must maintain detailed records on all subjects who sign the Informed Consent and begin the pre-procedure evaluation. Data for enrolled subjects will be entered into eCRFs provided by the Sponsor. All data should be entered completely, promptly and legibly. For source documents, corrections should be made in a manner that does not obscure or eliminate the original error, by striking through the original data with one line, and initialing and dating the change, along with the reason for the change (if not obvious).

Study Exit eCRFs are completed for all enrolled subjects, regardless of whether they completed all study requirements (e.g., subject discontinuation, trial termination).

## **11. Monitoring Procedures**

### ***11.1. Monitoring***

Monitoring visits to the clinical sites will be made periodically during the study, to ensure that all aspects of the current, approved protocol/amendment(s) are followed. Original source documents will be reviewed for verification of data in the electronic database. The Investigator/institution guarantees direct access to original source documents by Cardiva Medical, Inc. personnel, their designees, and appropriate regulatory authorities. In the event that the original medical records cannot be obtained for a patient that is seen by a non-study physician at a non-study institution, photocopies of the original source documents must be made available for review.

It is important that the Investigator and relevant study personnel are available during the monitoring visits and that sufficient time is devoted to the process.

Phone contacts and site visits will be conducted to ensure that the protocol is being followed and that any protocol deviations are properly documented. Clinical monitoring will include a verification that Informed Consent was properly obtained for all enrolled trial participants, a review of clinical records for accuracy and completeness, resolution of missing or inconsistent results and a review of source documents. The Monitor will verify that the Case Report Forms (eCRFs) are in agreement with the source documentation and other records. The Investigator will make available to the clinical monitor for review all Informed Consent documents, Internet access to completed eCRFs, source documentation, original laboratory data and other relevant records

for all enrolled subjects at the site. It is important that the Investigator and other relevant site personnel are available for consultation with the Monitors during the monitoring visits and that sufficient time is devoted at the site to the monitoring process.

Additionally, telephone and/or e-mail contact will be conducted on a regular basis with the Investigator and the site staff to ensure that the protocol is being followed and to address any issues that may occur during the course of the study. In some cases, remote monitoring and data cleaning may be performed.

If a deficiency is noted during an on-site visit (or at any other time during the course of the trial), the Monitor is required to discuss the situation with the Investigator and the Sponsor (if required) to secure compliance.

## ***11.2. Investigational Device Distribution and Accountability***

### **11.2.1. Investigational Device Distribution**

Cardiva Medical will provide and control the distribution of the investigational devices. Each investigational site will be responsible for ordering the investigational devices for the study. The Investigator is responsible for ensuring that the devices are ordered for shipment to arrive at the hospital before the procedure date.

Devices will be shipped with an Investigational Device Shipment Record. This form is to be used by Cardiva Medical and the investigational site to record any shipments of the investigational device. A copy is to be retained by the shipper and the recipient.

### **11.2.2. Device Accountability**

The Investigator shall maintain adequate records of the receipt and disposition of all investigational devices. The Investigator is responsible for ensuring that the investigational devices are used only under the Investigator's supervision and are only used according to this protocol and any approved amendments. The Investigator will not supply an investigational device to any person not authorized to participate in the trial. The Investigator shall document in the operative notes and eCRF's the lot number of the devices used during a case. In addition, the Investigator shall keep complete and accurate records of all devices used or unused that have been returned to Cardiva Medical in a Device Accountability Log provided by Cardiva Medical.

### **11.2.3. Return of Materials Upon Study Termination**

After the cases are completed, all unused devices must be accounted for and shipped back to Cardiva Medical. Instructions for device return to Cardiva Medical will be reviewed at the site initiation visit.

**IMPORTANT:** Please note that the devices must be labeled with a "BIOHAZARD" sticker if there is reasonable belief that the device has come in contact with blood or infectious substances that are known or are believed to cause disease in animals or humans. Refer to the Manual of Operations for Device Return Instructions.

## **12. Quality Control and Quality Assurance**

### **12.1. Site Training**

To ensure accurate, complete, and reliable data, the Sponsor or its representatives will provide instructional material to the trial sites, as appropriate and will:

- Instruct the Investigators and trial personnel on the protocol, the completion of the eCRFs, and trial procedures;
- Communicate regularly with site personnel via mail, email, telephone, and/or fax;
- Make periodic visits to the trial sites;
- Conduct periodic remote data cleaning and correspondence.

### **12.2. Investigator and Co-Investigator Training**

An Investigator is defined as the person responsible for the conduct of the clinical investigation at an investigational site. The Investigator is the responsible leader of the team and may be called the Principal Investigator.

A Co-Investigator is defined as an individual member of the clinical investigation team designated and supervised by the Investigator at an investigational site who performs critical investigation-related procedures and/or makes important investigation-related observations, including enrollment of subjects and deployment of the study device.

An Operator is defined as an individual member of the clinical investigation team who is qualified by training and experience (i.e., non-Investigator MD or certified vascular tech), and who is designated to deploy the study device in a study subject under the direction of, and the direct supervision of an Investigator or Co-Investigator.

Prior to enrolling any subjects in the study, Investigators, Co-Investigators and Operators will be provided didactic training with a benchtop model to simulate the closure procedure with the Mid-Bore Venous Vascular Closure System. This training will be provided by a Sponsor-designated proctor. Benchtop training will be followed by study device deployment under proctor in a roll-in subject for up to 4 of the femoral venous access sites. The proctor shall either approve, or require additional training for each individual until all pre-specified training requirements have been met.

Investigators and Co-Investigators will be notified in writing when they have successfully completed the roll-in requirements and are eligible to randomize subjects into the trial, and to deploy the study device without a Sponsor proctor. Operators will be notified in writing when they have successfully completed the roll-in requirements and are eligible to deploy the study device under the direct supervision of an Investigator/Co-Investigator in a consented, qualifying study patient without a Sponsor proctor. An Operator will not have authority to make any decisions about enrollment, but only to deploy the device as directed.

An Investigator and Operator Training & Proctor Log will be utilized to assess and ensure all skills and knowledge levels are satisfactory prior to written approvals by the Sponsor.

These roll-in subjects will be followed in the same fashion as the randomized subjects and evaluated as a separate subject cohort.

### **12.3. Audits and Inspections**

The Principal Investigator for the site will also allow representatives of the governing IRB, the United States Food and Drug Administration (FDA), and other applicable regulatory agencies to inspect all trial records, eCRFs, and corresponding portions of the subject's office and/or hospital medical records at regular intervals throughout the study. These inspections are for the purpose of verifying adherence to the protocol, completeness and exactness of the data being transcribed to the eCRF, and compliance with FDA or other regulatory agency regulations.

The Principal Investigator for the site will inform the Sponsor or the Sponsor's designee in advance if they are to be audited or inspected by any regulatory agencies. The Sponsor or the Sponsor's designee will also inform the site if they are made aware of a pending audit or inspection by a regulatory agency.

## **13. Adverse Events**

### **13.1. General**

All adverse events (AE) and serious adverse events (SAE) will be monitored from the time of randomization through the 1-month follow-up visit.

An AE is defined as any undesirable clinical occurrence in a patient whether or not it is considered to be device related. In addition, the definition of AE applies to any event with an onset post study procedure or to any underlying diseases present at baseline, that exacerbate in severity post study procedure. Therefore, an underlying disease that was present at the time of enrollment is not reported as an AE, but any increase in the severity of the underlying disease is to be reported as an AE. This definition includes events occurring during the follow-up period.

All reported AEs must be recorded in the electronic database. A description of the event, including the start date, resolution date, action taken, and the outcome should be provided, along with the Investigator's assessment of the relationship between the AE, the study treatment and the study procedure.

The following definitions for rating severity of adverse events will be used:

Mild:	Awareness of signs or symptoms, but easily tolerated; are of minor irritant type; causing no loss of time from normal activities; symptoms would not require medication or a medical evaluation; signs or symptoms are transient.
Moderate:	Interferes with the subject's usual activity and/or requires symptomatic treatment.
Severe:	Symptom(s) causing severe discomfort and significant impact of the subject's usual activity and requires treatment.

A serious adverse event (SAE) is defined as an event which leads to:

- Death due to any cause
- Life-threatening condition
- Results in persistent or significant disability/incapacity
- Requires in-patient hospitalization or prolonged hospitalization
- Results in congenital abnormality

All SAE's will be reported.

**Device-Related Adverse Event:** an adverse event is considered to be device-related when, in the judgment of the Investigator, the clinical event has a reasonable time sequence associated with use of the investigational device and is unlikely to be attributed to concurrent disease or other procedures or medications. It is reasonable to believe that the device directly caused or contributed to the adverse event.

**Procedure-Related Adverse Event:** an adverse event is considered to be procedure-related when, in the judgment of the Investigator, it is reasonable to believe that the event is associated with the assigned study procedure and is not specific to the investigational device used. Other products, surgical techniques, or medications required specifically for the procedure are likely to have contributed to the occurrence of the event.

**Concomitant Medication-Related Adverse Event:** an adverse event is considered to be concomitant medication related when, in the judgment of the Investigator, it is reasonable to believe that the event is associated with concomitant medications used in conjunction with the investigational device and is not otherwise specific to the investigational device (e.g. bleeding associated with anticoagulation medication).

**Pre-Existing Condition-Related Adverse Event:** an adverse event is considered to be related to a pre-existing condition when, in the judgment of the Investigator, it is reasonable to believe that the event is associated with the subject's pre-existing condition and is not specific to the investigational device or procedure. Pre-existing conditions that are aggravated or become more severe during or after the procedure should be evaluated on a case-by-case basis to determine if the event may be more appropriately classified as device-related or procedure-related.

Cardiva Medical, Inc., or its designee, in cooperation with the Investigator, will assess all adverse events considered to be device-related for potential reportability to the FDA and other regulatory authorities as an Unanticipated Adverse Device Effect (UADE).

The Investigator should follow all unresolved serious adverse events until the events are resolved, the subject is lost to follow-up, the subject has withdrawn consent, or the adverse event is otherwise explained.

**Non-Events:** For purposes of this study, the following events are not considered adverse events, because they are normally expected to occur in conjunction with catheter-based procedures / post-procedure, or are associated with customary, standard care of subjects undergoing these procedures:

- Early post-operative pain (within 24 hours post-index procedure) at the access site and/or related to position on procedure table
- Post-anesthesia/conscious sedation emesis, nausea, or headache (within 24 hours post-index procedure)
- Chest pain without associated ECG changes
- Hematocrit decrease from baseline not associated with hemodynamic changes, remaining above 30% and not requiring transfusion
- Electrolyte imbalance without clinical sequelae following endovascular procedure, even if requiring correction
- Low grade temperature increase ( $\leq 38.3^{\circ}\text{C}/\leq 101^{\circ}\text{F}$ )
- Sinus bradycardia/tachycardia that does not require treatment or intervention
- Systolic or diastolic blood pressure changes that do not require treatment or intervention
- Any pre-planned surgical procedures

This listing of events is intended to provide guidance to the investigational sites for purposes of adverse event reporting. The Investigator at the investigational site should utilize his/her own clinical judgment in evaluating adverse experiences, and may decide that the above events should be reported as adverse events.

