## **7. Study Procedures and Enrollment**

### ***7.1. Duration of Subject Participation***

Subjects enrolled in the trial will participate for approximately 30 (+/- 7) days.

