## **7.6. Study Exit**

Once the subject has completed the follow-up visit or has withdrawn, they should be exited from the study provided they do not have any conditions that require continued follow-up. The date of exit and subject status should be recorded on the Study Exit CRF.

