### **8.3. Primary Safety Endpoint**

On a **per-limb basis**, the rate of combined major venous access site closure-related complications through 30 days post-procedure, attributed directly to the closure method (i.e., “device-related” with no other likely attributable cause):

- Access site-related bleeding requiring transfusion;
- Vascular injury requiring surgical repair;
- Access site-related infection confirmed by culture and sensitivity, requiring intravenous antibiotics and/or extended hospitalization;
- New onset permanent access site-related nerve injury (i.e., persisting for > 30 days)
- New onset access site-related nerve injury in the ipsilateral lower extremity requiring surgical repair;
- Pulmonary embolism requiring surgical or endovascular intervention and/or resulting in death, to be confirmed by CT pulmonary angiography, lung ventilation/perfusion scan (VQ scan) or autopsy;
- Pulmonary embolism NOT requiring surgical or endovascular intervention and/or NOT resulting in death, to be confirmed by CT pulmonary angiography or lung ventilation/perfusion scan (VQ scan).

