#### 9.2.3. Safety

##### Primary Safety Analysis

The primary safety analysis will be based on the 30-day limb incidence rate of combined major access site closure complications (see 7.3). Both the combined rate and individual complication incidence rates will be reported by treatment received as described in 8.1.2.

The statistical hypotheses are as follows:

- $H_0$ : Cardiva Mid-Bore VVCS rate – manual compression rate  $\geq 5\%$
- $H_A$ : Cardiva Mid-Bore VVCS rate – manual compression rate  $< 5\%$

A 2-sided 95% confidence interval will be constructed by the bootstrap re-sampling method, with patient as the sampling unit as opposed to the limb, for the VVCS – manual compression

major complication rate difference. This is to account for an unlikely correlation between two limbs of a patient with respect to major closure complications. One million bootstrap resampling simulations will be performed. For each simulation, stratified sampling with replacement (by randomization stratification factor) will be performed separately for the two study arms and the VVCS – manual compression (MC) major complication rate difference will be recorded. With one million simulations, a data distribution will be generated for the VVCS – MC major complication rate difference. With patient as the sampling unit, any data structure (independent or correlated) between the same patient's two limbs is preserved in this data distribution. If the 97.5th percentile of the distribution, i.e. the upper limit of the 2-sided 95% confidence interval for the VVCS – MC difference, is <5%, then the null hypothesis of a ≥5% higher VVCS complication rate will be rejected at a 2-sided 0.05 significance level. In this case the VVCS major complications rate will be considered non-inferior to that of the manual compression.

As an example to illustrate the actual study results required in order to accomplish this goal, assume the two limbs within each patient to be independent (highly likely) and a 2% (4/204) major complication rate is observed for the MC control treatment. The observed VVCS major complication rate must be ≤ 3% (6/204) in order for the 95% confidence upper limit for the difference to be <5%. This confidence interval calculation is based on Newcombe's method derived from Wilson scores. (*Ref: Newcombe RG, Interval Estimation for the Difference between Independent Proportions: Comparison of Eleven Methods, Statistics in Medicine, 17, 8 73-890, 1998*).

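### The safety endpoint runs through day 30, but adverse event monitoring can end at a visit on day 23, so new major events after an early visit have no planned ascertainment and the limb counts as event-free

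*Combined protocol and SAP*

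**What the plan says.** - **Endpoint.** Section 8.3 sets it as "the rate of combined major venous access site closure-related complications through 30 days post-procedure", and Section 9.2.3 carries this into the test: "The primary safety analysis will be based on the 30-day limb incidence rate of combined major access site closure complications". The analysis is a crude proportion of limbs. It has no censoring and no minimum follow-up.
- **Monitoring.** Section 13.1: "All adverse events (AE) and serious adverse events (SAE) will be monitored from the time of randomization through the 1-month follow-up visit".
- **Visit timing.** Section 7.1: "Subjects enrolled in the trial will participate for approximately 30 (+/- 7) days". Table 3 and Section 7.5 use the same window, so an in-window visit can fall on day 23.
- **Exit.** Section 7.6 says that after the visit "they should be exited from the study provided they do not have any conditions that require continued follow-up".
- **Follow-up beyond the visit.** Section 13.1: "The Investigator should follow all unresolved serious adverse events until the events are resolved". Section 7.5 offers a telephone check only to subjects who cannot attend the visit.
- **Roll-in subjects.** They are not randomized. Section 12.2 says: "These roll-in subjects will be followed in the same fashion as the randomized subjects". Section 9.2 keeps them out of the formal analysis.

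**The concern.** The endpoint promises 30 days of observation for every limb, and the schedule does not require it. A subject seen on day 23 is fully compliant and may then be exited. If that subject has a pulmonary embolism, a culture-confirmed infection needing intravenous antibiotics or a transfused access site bleed on day 27, no planned contact would find it.

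The provisions that extend follow-up (Section 7.6 for conditions requiring it, Section 13.1 for unresolved serious events) apply to problems already known at the visit. The worst-case and tipping-point analyses in Section 9.1.3 do not help either. They act on missing data, and this subject's follow-up is recorded as complete.

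The direction matters because the test is one of non-inferiority on an absolute difference. If the same fraction of events is lost in both arms, the difference shrinks by that fraction and a fixed 5-point margin is easier to meet. Section 3 makes this test one of two conditions for trial success, and the plan expects only about four events per arm (204 × 0.02 = 4.08).

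**Working it through.** **Inputs from the documents.** Visit window 30 ± 7 days; endpoint through day 30; 102 patients (204 limbs) per arm; 2% major complication rate per limb in both arms; 5-point margin; percentile bootstrap by patient, passing if the 97.5th percentile is below 5%.

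**Inputs assumed.** The distribution of visit days and the timing of event onset are in neither the protocol nor the SAP sections, so ranges are shown.

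**1. Reproduce the plan's figures.** Enumerating two Binomial(204, 0.02) counts and summing the probability that the Newcombe upper limit is below 0.05 gives power 0.877, against the stated 0.88. The Newcombe limit for 6/204 versus 4/204 is 0.045, as in Table 5. For the bootstrap with events in different patients, the resampled count in an arm with x events is Binomial(102, x/102), divided by 204 limbs. For 6 versus 4 events this gives an upper limit of 0.039, the Sim 1 value in Table 5.

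**2. Length of the gap.** Earliest visit: 30 − 7 = day 23. At most 7 of 30 days (23.3%) are unobserved for one subject. Visits on days 30 to 37 leave no gap.

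**3. Share of events missed, visits even over the 15 days 23 to 37.**
- Subjects seen before day 30: 7/15 = 47%.
- Constant hazard: Σ(30 − d) for d = 23 to 29 is 28, and 28/(15 × 30) = 6.2%.
- Exponential onset with mean parameter m, truncated at day 30: F(t) = (1 − e^(−t/m)) / (1 − e^(−30/m)), and the missed share is (1/15) Σ[1 − F(d)] over d = 23 to 29. This gives 2.1% for m = 14 and 0.5% for m = 7.

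**4. Effect on the test at the margin.** Take a true 7% versus 2%, multiply both rates by (1 − share missed), and sum the probability that the bootstrap rule passes. Event counts are Binomial(204, rate), events fall in different patients, and the bootstrap is unstratified.

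| Scenario | Missed | Observed difference | Chance of passing |
|---|---|---|---|
| Full 30-day ascertainment | 0 | 5.0 points | 4.4% |
| Even visits, m = 7 | 0.5% | 5.0 points | 4.6% |
| Even visits, m = 14 | 2.1% | 4.9 points | 5.0% |
| Even visits, constant hazard | 6.2% | 4.7 points | 6.1% |
| All visits on day 23, constant hazard | 23.3% | 3.8 points | 14.4% |

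The 4.4% in the first row already exceeds 2.5%. That comes from the percentile bootstrap with few events, not from the visit window. The window's contribution is the increase over 4.4%.

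**5. Cross-check with Newcombe.** The same calculation goes from 2.3% with full ascertainment to 3.2% (even visits, constant hazard) and 8.0% (all on day 23). The direction and rough size are the same.

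**6. At the planned 2% in both arms.** A 6.2% loss removes 4.08 × 0.062 = 0.25 expected events per arm. The day 23 bound removes 4.08 × 0.233 = 0.95. Newcombe power would appear to rise from 0.877 to 0.891 and 0.925 respectively.

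**The case against.** **The plan may mean 30 ± 7 when it says 30 days.** Section 4.1 describes safety as assessed at 30 (+/- 7) days. On that reading the issue is visit tolerance and loose wording. This has force, and one sentence adopting that definition would settle the text. But Sections 8.3 and 9.2.3 state 30 days without tolerance, and limbs would still be observed for between 23 and 37 days in a crude rate.

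**The effect is probably small.** An event counts only if attributed directly to the closure method, which plausibly favours early onset. At a mean of 7 days the chance of passing moves from 4.4% to 4.6%. Visits clustered near day 30 also reduce the loss: with an assumed normal spread of SD 3 days it is 3.8% even at constant hazard. The earlier arterial closure trial in Table 1 had no major events in either arm. All of this stands and limits the weight of the point.

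**Two stronger readings that the documents do not support.**
- A reader might infer that adverse events are not collected for roll-in subjects, because monitoring starts at randomization. Section 12.2 gives them the same follow-up as randomized subjects, Section 9.2 summarizes their results, Section 13.1 defines an adverse event by onset after the study procedure, and Section 13.2.1 is not limited to randomized subjects. Only their stated start point is unclear, and they do not enter the primary test.
- A reader might count late access site bleeding among the losses that ease the non-inferiority test. It is a minor complication (Section 8.4), and Section 9.2.3 plans no formal test of those.

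**Conclusion.** The point holds in a limited form. A new major event between an early visit and day 30 has no planned ascertainment, yet the limb is analyzed as event-free rather than missing. If loss is proportional in both arms, this biases the absolute difference toward zero and slightly favours non-inferiority. If onset timing differed between arms, the bias could be larger, smaller or reversed, and the documents give nothing to judge that.

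The size cannot be determined from the documents. With visits even over days 23 to 37, the loss is 0.5% to 6.2% of events, and the chance of passing at a true 7% versus 2% rises from 4.4% to between 4.6% and 6.1%. The 14% figure is a bound that needs every visit on day 23 and constant hazard, and should not be read as an expectation. The likely effect is small, but the change is cheap and protects a rare-event endpoint on which trial success depends.

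**What to change.** 1. Set the follow-up window to day 30 to day 37. Alternatively, keep 30 ± 7 and, for visits on days 23 to 29, add a brief telephone safety check on or after day 30, with study exit (Section 7.6) only after that check. Section 7.5 already uses a telephone check for subjects who cannot attend.
2. State in Section 13.1 that adverse event monitoring runs through the later of the follow-up visit and day 30.
3. As a wording clarification only, anchor the start of monitoring for roll-in subjects to the index closure procedure.

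The cost is amendment wording, plus either one week less scheduling flexibility or a short call for subjects seen early. No patients or procedures are added.
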